10.3.1.9 Documentation of particular situations

AEs that are secondary to other events

In general, AEs that are secondary to other events (e.g., cascade events or clinical sequelae) should be identified by their primary cause, with the exception of severe or serious secondary events. A medically significant secondary AE that is separated in time from the initiating event should be documented as an independent AE in source data and eCRF. For example:

If vomiting results in mild dehydration with no additional treatment in a healthy adult, only vomiting should be documented as AE.

If vomiting results in severe dehydration, both events should be documented as AEs separately.

Abnormal laboratory results and vital signs values

Not every laboratory or vital signs abnormality needs to be documented as AE. For clinically significant laboratory/vital signs abnormalities the following definitions and documentation rules apply:

- If a laboratory/vital signs abnormality is a sign of a disease or syndrome, the laboratory/vital signs abnormality is clinically significant and only the diagnosis of the causing disease or syndrome needs to be documented as AE.
- If a laboratory/vital signs abnormality results in specific symptoms but no diagnosis of a disease or syndrome can be made, the laboratory/vital signs abnormality is clinically significant and only the symptoms need to be documented as AEs.
- If a laboratory/vital signs abnormality is not a sign of a disease or syndrome and does not result in specific symptoms but leads to a change in trial treatment or in a medical intervention, the laboratory/vital signs abnormality is clinically significant and must be documented as AE.

AEs associated with an overdose or error in drug administration

An overdose is the accidental or intentional use of a drug in an amount (per administration or cumulatively) higher than the dose being studied (for the trial treatment) or higher than the maximum recommended dose according to the authorized product information (for approved concomitant medications). An overdose or incorrect administration of a drug is not itself an AE, but it may result in an AE.

All AEs associated with an overdose or incorrect administration should be documented as AE in source data and eCRF and reported as SAE if applicable.

10.3.1.10 Reporting of serious adverse events

All SAEs which occur in a patient during the observation period, whether considered to be associated with trial treatment or not, must be reported by the investigator to the sponsor within 24 h following knowledge of the event.

Page 112 of 133 Version: 7.0 Date: 09 FEB 2023

All SAEs occurring after the end of the period of observation only have to be reported to the sponsor within the appropriate time frame if the investigator suspects a relationship to trial treatment or the trial procedure.

SAE reporting to the sponsor using a paper (SAE report) form

For the period of observation please refer to Section 8.3.1.

The investigator needs to complete the paper Serious Adverse Event Form which must be sent to the sponsor via one of the following reporting lines:

Safety report fax no.:Safety report E-mail address:

Information for final description and evaluation of a case report may not be available within the required time frames for reporting. Nevertheless, for regulatory purposes, initial reports should be submitted if the following minimal information is available:

- An identifiable patient (patient number)
- A suspected medicinal product
- An identifiable reporting source (investigator/trial site identification)
- An event or outcome that can be identified as serious

SAE follow-up information should be sent to the sponsor (indicating that this is a "follow-up" report using the SAE Form or the Additional Information and Follow-Up Form) without delay as described above and accompanied by appropriate anonymous supporting documentation (e.g., discharge letters, medical reports or death certificates), until a final outcome and date are available. All confidential information (name, address, full day of birth) needs to be blackened before sending. In addition to a medical record, the investigator should complete an Additional Information and Follow-Up Form, which contains the SAE term and patient number.

A copy of the submitted SAE report must be retained on file by the investigator. If explicitly required according to national legislation, the investigator must submit copies of the SAEs to the IRB/IEC or authority and retain documentation of these submissions in the Site Trial File.

In case an investigator or any other trial team member has questions on safety reporting the sponsor may be contacted via:

•	E-mail:								
1: .	1 4:	41	 :4	£ 41- ! -	4	- -	L .	4 _	_4_

For medical questions, the medical monitor for this trial should be contacted.

Page 113 of 133 Version: 7.0 Date: 09 FEB 2023

10.4 Contraceptive guidance and collection of pregnancy information

10.4.1 Definitions

Definition of reproductive potential and measures of contraception for BNT111 are detailed below. Further guidance for other trial treatments should be according to the authorized product information (for approved concomitant medications).

Female patients

In this trial, female patients are considered to be WOCBP, unless they are post-menopausal or permanently sterile:

- A post-menopausal state is defined as no menses, in patients > 45 years of age, for 12 months without an alternative medical cause. A high follicle stimulating hormone (FSH) level in the post-menopausal range may be used to confirm a post-menopausal state in patients not using hormonal contraception or hormonal replacement therapy. However, in the absence of 12 months of amenorrhea, a single FSH measurement is insufficient.
- Permanent sterilization methods include hysterectomy, bilateral salpingectomy and bilateral oophorectomy.

All female patients must agree not to donate eggs (ova, oocytes) for the purpose of assisted reproduction during the trial and for 6 months after receiving the last dose of BNT111.

Female patients of reproductive potential must agree to use adequate contraception during and for 6 months after the last BNT111 administration. Adequate contraception is defined as highly effective methods of contraception (Table 15). Birth control methods are considered highly effective if they have a failure rate of less than 1% per year, when used consistently and correctly.

The investigator or delegate should advise the patient how to achieve effective contraception as outlined in Table 15.

Table 15: Highly effective methods of contraception

- Combined (estrogen and progestogen containing) hormonal contraception associated with inhibition of ovulation¹ (oral, intravaginal, or transdermal) in combination with a barrier method or/and an intrauterine device.
- Progestogen-only hormonal contraception associated with inhibition of ovulation¹ (oral, injectable, or implantable) in combination with a barrier method or/and an intrauterine device.
- Intrauterine device²
- Intrauterine hormone-releasing system²
- Bilateral tubal occlusion²
- Vasectomized partner^{2, 3}
- Sexual abstinence⁴

BioNTech SE Confidential

Clinical Trial Protocol BNT111-01

Page 114 of 133 Version: 7.0 Date: 09 FEB 2023

- 1. Hormonal contraception may be susceptible to interaction with some concomitant medications, which may reduce the efficacy of the contraception method.
- 2. Contraception methods that in the context of this guidance are considered to have low user dependency.
- 3. Vasectomized partner is a highly effective birth control method provided that partner is the sole sexual partner of the woman of childbearing potential (trial patient) and that the vasectomized partner has received medical assessment of the surgical success.
- 4. In the context of this guidance sexual abstinence is considered a highly effective method only if defined as refraining from heterosexual intercourse during the entire period of risk associated with the trial treatments. The reliability of sexual abstinence needs to be evaluated in relation to the duration of the clinical trial and the preferred and usual lifestyle of the patient.

Table adapted from 'Recommendations related to contraception and pregnancy testing in clinical trials'. Advisory non-binding guidance represented at the Clinical Trial Facilitation Group (CTFG)-meeting in Rome 2014 (CTFG 2014).

Male patients

Recommendations for male patients with pregnant partner:

Male contraception (condom) is recommended in order to avoid exposure of an existing embryo/fetus. Contraception should be continued for 6 months after receiving the last dose of BNT111.

Recommendations for male patients with non-pregnant WOCBP partner:

The male patient should use condom during treatment and for 6 months after receiving the last dose of BNT111. For a non-pregnant WOCBP partner, contraception recommendations should also be considered.

Male patients must also not donate sperm during the trial and for 6 months after receiving the last dose of BNT111.

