 - a. Female patients of reproductive potential must agree to use highly effective contraception during and for 6 months after the last trial drug administration (Section 10.4).
- 19. WOCBP must agree not to donate eggs (ova, oocytes) for the purposes of assisted reproduction during trial starting at screening, during the trial and for 6 months after receiving the last trial treatment.
- 20. A man who is sexually active with a WOCBP and has not had a vasectomy must agree to use a barrier method of birth control, e.g., either condom with spermicidal foam/gel/film/cream/suppository or partner with occlusive cap (diaphragm or cervical/vault caps) with spermicidal foam/gel/film/cream/suppository, and all men must also not donate sperm during the trial and for 6 months after receiving the last trial treatment. For a definition of adequate contraception, see Section 10.4.

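### Protocol Section 10.4.1 counts the 6-month contraception and donation period from the last BNT111 dose, while the eligibility criteria and Section 8.3.5 count it from the last dose of trial treatment

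*Protocol*

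**What the plan says.** Protocol Section 10.4.1 opens by limiting its contraception measures to BNT111. It then adds: "Further guidance for other trial treatments should be according to the authorized product information (for approved concomitant medications)". Five clauses follow, each with a 6-month tail counted from BNT111:

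- Egg donation, barred "for the purpose of assisted reproduction during the trial and for 6 months after receiving the last dose of BNT111".
- Female contraception: "Female patients of reproductive potential must agree to use adequate contraception during and for 6 months after the last BNT111 administration".
- Men with a pregnant partner: "Contraception should be continued for 6 months after receiving the last dose of BNT111".
- Men with a non-pregnant partner of childbearing potential: "The male patient should use condom during treatment and for 6 months after receiving the last dose of BNT111".
- Sperm donation: "Male patients must also not donate sperm during the trial and for 6 months after receiving the last dose of BNT111".

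Elsewhere the tail has the same length but a different start. Under inclusion criterion 18a (Section 5.1.1), women of reproductive potential "must agree to use highly effective contraception during and for 6 months after the last trial drug administration". Criteria 19 and 20 and add-on criteria 5 and 6 (Section 5.1.3) count from the last trial treatment. Add-on criterion 4 counts from the last trial drug. Section 8.3.5 also counts from the last trial drug, for contraception in both sexes.

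**The concern.** Cemiplimab is a trial treatment in its own right: Section 6.1 classes both drugs as investigational medicinal products. The last BNT111 dose and the last dose of trial treatment are therefore not always the same day. Section 6.3 allows one drug to continue when the other is discontinued. Section 6.8.2 lists stopping rules specific to BNT111, such as a first anaphylaxis or a Grade 4 injection-related reaction.

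For a patient who stops BNT111 and stays on cemiplimab, a site that takes the end date from the contraception section could give one earlier than the date in the criteria the patient agreed to. Criterion 18a and add-on criterion 4 cite Section 10.4 directly after stating the period, so a site following that reference finds a different start date. What is at stake is a reproductive-safety instruction. No endpoint or analysis depends on it.

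**Working it through.** The documents give no figure to reproduce, so the check compares the clauses and then works out how far apart the dates can be.

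**Start of the 6 months, side by side**

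| Rule | Section 10.4.1 | Criteria | Section 8.3.5 |
|---|---|---|---|
| Female contraception | last BNT111 | last trial drug (18a, add-on 4) | last trial drug |
| Egg donation | last BNT111 | last trial treatment (19, add-on 5) | not covered |
| Male contraception | last BNT111 (two clauses) | barrier method and sperm donation in one sentence, last trial treatment (20, add-on 6) | last trial drug |
| Sperm donation | last BNT111 | last trial treatment (20, add-on 6) | not covered |

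All five clauses of 10.4.1 use BNT111. All six criteria and both statements in 8.3.5 use trial drug or trial treatment. The length is 6 months throughout.

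**Size of the gap.** Let s be the month of the last BNT111 dose and T the month of the last cemiplimab dose, with s ≤ T.

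- End date under 18a and 8.3.5: T + 6.
- End date under 10.4.1, with cover running throughout treatment: max(T, s + 6).
- Shortfall: T + 6 − max(T, s + 6) = min(6, T − s), all of it after the last cemiplimab dose.

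| T (assumed) | s (assumed) | 10.4.1 end | Criteria end | Shortfall (months) |
|---|---|---|---|---|
| 24 | 3, 6, 12 or 18 | 24 | 30 | 6 |
| 24 | 21 | 27 | 30 | 3 |
| 24 | 24 | 30 | 30 | 0 |
| 6 | 3 | 9 | 12 | 3 |

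T = 24 is the maximum treatment duration in Section 6.3. The other values are illustrations.

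This applies to female contraception and to condom use with a non-pregnant partner. In the female clause the word *during* has no object. Neighbouring clauses refer to the trial or to treatment, and footnote 4 of Table 15 defines abstinence as "refraining from heterosexual intercourse during the entire period of risk associated with the trial treatments", so during treatment is the natural reading. If *during* meant BNT111 dosing only, the 10.4.1 end date would be s + 6. It would then fall while cemiplimab is still being given only if T − s exceeds 6 months.

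**Other clauses.** The donation bans also run for the whole of trial participation. There is no shortfall while the patient remains in the trial, and at most 6 months if the patient leaves at the last cemiplimab dose. The pregnant-partner clause is a recommendation tied to an existing pregnancy, so no months are claimed for it.

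**By arm** (patient numbers from SAP Table 3.2)

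- Arm 1 (90 patients) and add-on patients: affected only if BNT111 stops first.
- Arm 2 without add-on: no discrepancy, because BNT111 is the only trial drug received.
- Arm 3 without add-on: no BNT111 dose and so no 10.4.1 date. This is at most 45 of 180 patients (45/180 = 25%), both sexes counted. Sections 5.1.1 and 8.3.5 cover them.

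**The case against.** The strongest reply is that 10.4.1 declares its scope. It covers BNT111 and sends other trial treatments to product information. Cemiplimab is the only other trial treatment and is an approved product, so counting BNT111 measures from BNT111 would be consistent. This explains the wording but does not settle the conflict. The referral's own parenthesis confines it to approved concomitant medications, and Section 10.3.1.9 uses the same phrase as the contrast to trial treatment. Where the protocol means the cemiplimab label it names the drug, as in Section 10.6. Even if the referral does reach cemiplimab, 10.4.1 gives no period for it, while the criteria and 8.3.5 do.

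Several other points stand and limit the finding:

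- The two sets of rules can be met together. A patient who follows the criteria or 8.3.5 on contraception, and the criteria on donation, also meets 10.4.1.
- Criterion 20 and add-on criterion 6 cite Section 10.4 only for what counts as adequate contraception. Only 18a and add-on 4 cite it next to the period.
- Continuing cemiplimab alone needs investigator and sponsor agreement (6.3). Toxicity that cannot be attributed to one drug also interrupts or stops cemiplimab (6.8.2).
- The 25% for Arm 3 counts patients for whom 10.4.1 gives no date. It is not a count of patients at risk.
- What patients are actually told is in the consent form, and any cemiplimab-specific period is in its label. Neither is available here.

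**Conclusion.** The inconsistency is real and confined to Section 10.4.1. Confidence in the wording conflict is high. Its severity is minor, because the binding criteria and 8.3.5 already set the longer period for every arm.

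For a patient who stops BNT111 before cemiplimab, the date in 10.4.1 is early by min(6, T − s) months, so by at most 6. This assumes cover throughout treatment and a site that relies on 10.4.1 alone. The documents do not say how many patients would stop BNT111 alone or how many are women of childbearing potential, so the number affected cannot be estimated. Endpoints, sample size and analyses are untouched.

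**What to change.** Make three wording changes in Section 10.4.1:

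1. In all five clauses, require the measure during trial treatment (for the two donation bans, during the trial) and for 6 months after the last dose of trial treatment, BNT111 or cemiplimab, whichever is later. This also gives *during* an object in the female clause.
2. Widen the opening scope from BNT111 to both trial treatments.
3. Replace the referral to product information for concomitant medications with a sentence naming cemiplimab, for example: *If the locally approved cemiplimab label requires a longer period, the longer period applies.*

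The cost is a text edit in one protocol section. Eligibility, visits and analysis do not change, and every arm then has a defined end date that agrees with the criteria and Section 8.3.5.

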10.4.2 Collection of pregnancy information

Pregnancy information will only be collected after obtaining written informed consent from the pregnant female patient (or if a male patients' partner becomes pregnant, written informed consent from both).

Pregnancy information will be collected for pregnancies that occurred after the start of trial intervention and until 90 days after the last trial treatment for pregnant patients (or until 28 days after the last dosing of the male patient for pregnant female partners).

The initial and follow-up information must be documented on the paper-based Pregnancy Reporting Form and submitted to the sponsor within 24 h of knowledge of a patient's pregnancy/partner's pregnancy. The completed form needs to be sent to the Safety Report Fax number or E-mail given in Section 10.3.1.10. Completed pregnancy forms must be signed by an investigator before faxing/mailing them to the sponsor. Blank reporting forms are provided to the investigator during the site initiation visit and are filed in the investigator's site file (ISF).

The investigator will collect follow-up information on the patient/patient's partner and the neonate and the information will be forwarded to the sponsor. Pregnancy follow-up should describe the outcome of the pregnancy, including any voluntary or spontaneous

Page 115 of 133 Version: 7.0 Date: 09 FEB 2023

termination, details of the birth, the presence or absence of any congenital abnormalities, birth defects, maternal or newborn complications and their presumed relation to the IMPs. Generally, the follow-up will be of a duration determined in consultation with the pediatrician.

While pregnancy itself is not considered to be an AE or SAE, any pregnancy complication or elective termination of a pregnancy will be reported as an AE or SAE.

A spontaneous abortion is always considered to be an SAE and will be reported as such. Any post-trial pregnancy related SAE considered reasonably related to the trial intervention by the investigator will be reported to the sponsor within the appropriate time frame. While the investigator is not obligated to actively seek this information in former trial patients, he or she may learn of an SAE through spontaneous reporting.

10.5 Genetics

Genetic analyses will be performed as outlined in Section 8.8.

10.6 Liver safety: suggested actions and follow-up assessments

Based upon data from other studies using RNA-LPX formulations (refer to the BNT111 IB), the sponsor does not expect to encounter any liver safety issues.

For cemiplimab, please refer to the locally approved label.

10.7 Investigators and trial administrative structure

10.7.1 Investigators and trial site personnel

There must be an investigator at each trial site.

If the trial is conducted by a team of individuals at the trial site, the investigator leading and responsible for the team is called the principal investigator.

All persons assigned responsibility as principal investigator must sign a declaration of their responsibilities and their agreement to this protocol before any trial-related procedure is performed.

Curriculum vitae and/or other relevant documents confirming the current qualification of the investigators must be provided to the sponsor. This should include any previous training in the principles of GCP, experience obtained from work with clinical trials, and experience with patient care.

Documentation of all involved investigators must be maintained according to GCP and applicable regulatory requirements.

10.7.2 Trial site personnel assigned trial-related duties

The principal investigator may define appropriately qualified personnel at a trial site to perform significant trial-related procedures and/or to make trial-related decisions under

Page 116 of 133 Version: 7.0 Date: 09 FEB 2023

his/her supervision. In this case, the principal investigator must maintain a signed list of the persons to whom they delegate significant trial-related duties/responsibilities; the delegated trial-related duties/responsibilities must be specified in the list.

When personnel or responsibility changes are made, the principal investigator must ensure that the relevant documentation is updated before any trial-related activities are performed.

Documentation of all involved trial site personnel performing significant trial-related procedures and/or making trial-related decisions must be maintained according to GCP and applicable regulatory requirements.

10.7.3 Contract research organizations

Documentation of all involved CRO must be maintained according to GCP and applicable regulatory requirements. This includes documentation of any delegation of responsibilities to CROs.

10.7.4 The sponsor and sponsor's personnel

The trial sponsor listed on the title page accepts the responsibilities of the sponsor according to GCP and applicable regulatory requirements.

The sponsor must designate appropriately qualified personnel to advise on trial-related topics. The trial site will be provided with contact details for these personnel before any trial-related procedure is performed.

A list of key sponsor personnel involved in the preparation of this protocol and the conduct of the trial, including their full names, titles, roles, and responsibilities, must be maintained.

10.8 Country-specific requirements

Country-specific requirements will be met; specific information is not available as the sites have not yet been defined.

Page 117 of 133 Version: 7.0 Date: 09 FEB 2023

10.9 Other standard abbreviations and definitions

For trial-specific abbreviations, see the list of trial-specific abbreviations.

For definitions related to safety, see Section 10.3.

Abbreviation	Explanation
AE	Adverse event
CFR	(US) Code of Federal Regulations
CIOMS	Council for International Organizations of Medical Sciences
CRO	Contract research organization
d	Day(s)
eCRF	Electronic case report form
GCP	Good Clinical Practice
h	Hour(s)
ICF	Informed consent form
ICH	International Conference on Harmonisation (of technical requirements for registration of pharmaceuticals for human use)
IDMC	Independent data monitoring committee
IEC	Independent ethics committee
IMP	Investigational medicinal product
IRB	Institutional review board
(ir)RECIST	(Immune-related) Response Evaluation Criteria in Solid Tumors
ISF	Investigator's site file
min	Minute(s)
NCI-CTCAE	US National Cancer Institute Common Terminology Criteria for Adverse Events
PRO	Patient-reported outcomes
QoL	Quality of life
SAE	Serious adverse event
SoA	Schedule of activities
SOP	Standard operating procedure (used as synonym for all procedural documents)
SUSAR	Suspected unexpected serious adverse reaction
TEAE	Treatment-emergent adverse event
TMF	Trial master file
US	United States (of America)
Wks	Week(s)
WOCBP	Women of childbearing potential

Page 118 of 133 Version: 7.0 Date: 09 FEB 2023

